#### 9.2.1. Case report forms

Data related to the primary outcomes (PASS score), clinical outcome and health resource utilization will be entered directly into electronic CRFs using REDCap, licensed by Aalborg University Hospital, and saved electronically. All forms are filled out during (or immediately after) the assessment of a subject and must be legible. Errors and corrections are logged as provided by the REDCap interface. It is possible to export validated data from REDCap to e.g. a statistical program (e.g. STATA) for further statistical analysis. When data have been entered, reviewed, and verified the data will be frozen to prevent editing. Digitalized data are backed up and stored on specific drives at each site under the responsibility of the principal investigators for a minimum of 5 years after the study has ended.

#### 9.2.2. Source data identification and protection

A Patient Identification List containing patient number, full name, civil registration number for all participants included in the study is created, and ethics according to "databeskyttelsesforordningen" and "databeskyttelsesloven" is ensured. The list is populated and updated by a project nurse or other competent

person. A list of all source documents will be devised at the initiation of the study. All source documentation will be stored on a secure drive under the responsibility of the principal investigator.

### 9.3. Statistical methods

A repeated measures linear mixed effects model will be used for the primary analysis and will include terms for treatment group, assessment time point (day after randomization), and the interaction of treatment with assessment time point. Summary statistics and trend curves of PASS scores will be provided for the individual time points, and the difference in PASS scores between groups 48 hours after randomization is considered the primary efficacy parameter. Subgroup and covariate analyses will be performed if applicable and in case differences in patient subgroups deemed clinically relevant are evident. The primary analysis will be by intention to treat and in case of early hospital discharge or other reasons for missing values, the Last-Observation-Carried-Forward method will be employed. Trends in PASS and other secondary endpoints assessed consequently during the treatment period (biochemical tests and clinical outcome parameters) are analyzed using linear random-effects models and results presented as fitted trend curves. Outcomes assessed at single time points (baseline characteristics, CT features and gut permeability) are compared using Student's t-test or non-parametric analysis for continues data as appropriate. Binary outcomes will be analyzed using Fisher's exact test. All secondary endpoints will be analyzed by per-protocol.

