## 7.5. Participant timeline

### 7.5.1. Study days

A detailed description of the study procedures is illustrated in Table 1. Patients will be evaluated daily during admission by medical personnel and treated in agreement with the IAP/APA evidence-based guidelines for the management of AP (2). As part of the study, they will receive daily infusions with methylnaltrexone or matching placebo, and have the following examinations performed: i) clinical outcome and patient symptoms will be evaluated by means of both well-validated questionnaires and information from the patient's medical records (see section 9.1.2.), ii) the PASS score will be obtained daily and used to document the primary endpoint 48 hours after randomization, iii) blood samples (including C-Reactive Protein (CRP), interleukin (IL)-6, IL-8, IL-18, tumor necrosis factor alpha (TNF- $\alpha$ ) and cluster of differentiation 163 (CD163)) will be drawn

daily with the purpose of evaluating the systemic inflammatory response, and iv) an abdominal contrast-enhanced CT study will be performed at inclusion and after conclusion of treatment at day 5 (+/- 1 day) to document the presence and extent of pancreatic inflammation, fluid collections and necrosis according to the definitions given in the revised Atlanta criteria (20). As an integrated part of the CT exam at day 5 (+/- 1 day) patients will undergo assessment of the colon/gut transit time using radiopaque markers given orally in the morning on day 3 up to the planned CT exam. Finally, the intestinal permeability will be evaluated by a polyethylene glycol (PEG) 400/4000 test (see section 9.1.5.) 48 hours after randomization. At hospital discharge, patients are invited for a follow-up visit on day 14 (+/- 2 days) after randomization where the outcomes assessed during hospital admission (blood test and questionnaires including the PASS score) will be reassessed. Patients ready for discharge prior to completing five days treatment with methylnaltrexone will be handled according to the following:

- < 48 h of treatment: All data collection will be terminated upon discontinuation of the study medication and participant is regarded as dropout.

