2.2. Secondary Objectives and Outcomes

The secondary objective is to document the effects of methylnaltrexone treatment on several clinical outcomes in patients with acute pancreatitis.

The secondary outcomes are listed below:

- Difference between treatment groups (methylnaltrexone or placebo) in daily PASS-scores during treatment and at 14-day follow-up
- Difference between treatment groups on disease severity assessed using the revised Atlanta criteria (10), where patients are put into one of three categories (mild/moderate/severe)
- Difference between treatment groups on subjective measures of pain intensity and gastrointestinal function assessed using validated questionnaires (13–15) daily during treatment and at 14-day follow-up
- Difference between treatment groups in length of admission and mortality, assessed retrospectively 90 days after admission, using the patients' medical records

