2.3. Exploratory Objectives

The exploratory objectives are to examine the effects of methylnaltrexone treatment on the immune system, the gastrointestinal tract, and the pancreas. This is to examine whether treatment with methylnaltrexone may reverse potentially opioid-induced changes to these organs.

The exploratory outcomes are listed below:

- Difference between treatment groups on daily levels of circulating pro- and anti-inflammatory blood markers during treatment and at 14-day follow-up
- Difference between treatment groups in intestinal permeability measured based on the polyethylene glycol (PEG) 400/4000 test (16). Following ingestion of a PEG solution containing 5 g PEG 400 and 5 g PEG 4000 dissolved in 100 ml water, patients will have their urine collected for 24 hours. The small size molecules (PEG 400) traverse the intestinal barrier freely, independent of barrier function loss, whereas the large size molecules (PEG 4000) only cross the intestinal wall and becomes detectable in urine in

case of intestinal barrier function loss. Based on the ratio between the two molecules measured in the urine, we can approximate the intestinal permeability

- Difference between treatment groups on gut transit time assessed using a CT-based radiopaque marker method, where the patients are asked to ingest a capsule containing radiopaque markers 48 hours prior to a CT scan. Based on the location of the markers on the CT-scan, the transit time can be approximated
- Difference between groups on the prevalence of pancreatic complications assessed and quantified using a CT-scan according to the Atlanta criteria (10)

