2.5. Specification of endpoints

The primary outcome at the primary endpoint will be analyzed by intention-to-treat (ITT), whereas the secondary endpoints will be per-protocol (PP) analyses. Several factors such as treatment effect of methylnaltrexone and possible side-effects (17) may lead to an uneven distribution between excluded patients in the treatment groups (e.g. if methylnaltrexone patients are discharged earlier or discontinue treatment due to side effects). The ITT-analysis will protect against the potential bias of excluding patients unevenly according to which treatment they received. Only if the participant is randomized but never receives treatment, will they be excluded from the ITT-analysis.

The PP-analysis aims to uncover the treatment effect under ideal conditions in terms of treatment duration and follow-up. Furthermore, the PP-analysis is expected to provide mechanistic insights into the role of opioids and opioid antagonism in acute pancreatitis. Participants are included in the PP-analysis, when:

1. > 75 % of the study drug has been given
2. No major protocol deviations have been recorded

The trial is designed as a superiority trial, and we expect to see an effect of treatment after 48 hours of treatment – which is the explanation for choice of primary endpoint. Thus, we expect that the group allocated to the methylnaltrexone treatment, compared to the usual care group, will have:

1. Reduced disease severity (lower PASS-scores, lower prevalence of severe disease)
2. Improved clinical outcomes (lower pain scores, shorter admission lengths, reduced mortality, inflammatory cytokines/intestinal permeability/transit times closer to normal range, reduced prevalence of pancreatic complications)

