6.3. Major Protocol Deviations

It is expected that a proportion of the patients included into the study, will recover before 5 days have passed and thus be discharged before completing the study protocol. In case of early discharge, data handling of both primary and secondary outcomes be stratified according to table 2:

< 48 hours of treatment	All data collection will be terminated upon discontinuation participant is regarded as dropout.
\geq 48 hours of treatment, but discharge before day 5	Participant will be lost to follow-up on the following outcomes: daily PASS scores, blood samples, vital signs. The participant will be asked to complete questionnaires at home, and they will be offered a follow-up CT scan in an outpatient setting on day 5 (+/- 1 day). Furthermore, they will be invited to participate in the 14-day follow-up and mortality will be registered retrospectively.

Table 2

For the statistical analyses, the Last-Observation-Carried-Forward method will be employed in case of early hospital discharge or other reasons for missing values. We expect most missing values to be a consequence of early discharge (~ recovering early from their disease) and thus the Last-Observation-Carried-Forward method will reflect this by carrying forward a value corresponding to low disease activity after discharge, which we find to be a fair assumption. If this is not the case, e.g. if a lot of missing values are due to severe disease, we will consider using other methods for imputation of missing values.

7. Implementation of Analysis Plan

A monitor will be allocated from the good clinical practice (GCP) unit at Aarhus and Aalborg University Hospitals, and the responsible monitor will contact and visit the principal investigator on a regular basis. The monitor will be authorized to inspect the different study records (CRFs,

Aalborg, Denmark

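### As worded, the SAP's last-observation-carried-forward rule would fill a missed 14-day visit with an in-hospital value nominally nine or more days old

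*Protocol*

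**What the plan says.** The general rule is in SAP 6.3: "For the statistical analyses, the Last-Observation-Carried-Forward method will be employed in case of early hospital discharge or other reasons for missing values". It names no outcome and no visit, and sets no limit on how far a value may be carried. Protocol 9.3 has the same trigger ("in case of early hospital discharge or other reasons for missing values, the Last-Observation-Carried-Forward method will be employed"), but inside the sentence that sets intention to treat for the primary analysis. Protocol 7.5.1 mentions LOCF only for patients treated for at least 48 hours and discharged before day 5. Protocol 9.3.2 leaves missing-data handling to the SAP, so the wider SAP wording governs.

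Day 14 is analysed. SAP 2.2 lists as secondary the difference "in daily PASS-scores during treatment and at 14-day follow-up", and pain and gut-function questionnaires at the same times. SAP 2.3 lists as exploratory the daily levels of "circulating pro- and anti-inflammatory blood markers during treatment and at 14-day follow-up". The visit is by invitation: "At hospital discharge, patients are invited for a follow-up visit on day 14 (+/- 2 days) after randomization" (Protocol 7.5.1). Protocol Table 1 shows nothing between 120±2 hours and 14±2 days.

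The SAP's reason is that most missing values will come from early recovery, so that LOCF means "carrying forward a value corresponding to low disease activity after discharge". If that proves wrong, for example because many values are missing through severe disease, other imputation will be considered. None is named.

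**The concern.** A rule written with early discharge in mind extends, by its wording, to a visit for which that reasoning was not made. A patient who completes treatment and misses day 14 would have a score taken in hospital, during or just after the infusion, analysed as a day-14 outcome. PASS counts intravenous morphine dose, pain, diet intolerance and SIRS criteria, all of which can plausibly be higher in hospital than at an outpatient visit. The stated rationale is about disease activity and does not discuss cytokine levels at all.

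Three things could follow. A treatment difference present at 120 hours would partly reappear as a day-14 difference. Unequal attendance would create a difference of its own. And the wide spread of in-hospital scores would be mixed into the narrower day-14 distribution, which can hide a real effect.

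**Working it through.** **Age of the carried value.** Age = 14 days − (hour of last assessment ÷ 24), with the ±2-day and ±2-hour windows from Table 1.
- Last assessed at 120 h: 14 − 5 = 9 days. Window: 12 − 122/24 = 6.9 to 16 − 118/24 = 11.1 days.
- Last assessed at 48 h: 14 − 2 = 12 days. Window: 12 − 50/24 = 9.9 to 16 − 46/24 = 14.1 days.

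**Per-protocol set.** Secondary endpoints are per-protocol, which needs "> 75 % of the study drug has been given" (SAP 2.5). If that means the planned 5 days, it is more than 0.75 × 120 = 90 h of infusion. The last in-hospital score is then mostly from 96 h or 120 h, so 9 to 10 days old. The SAP does not state the analysis set for exploratory markers.

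**The plan's own figure.** The sample size reproduces: 2 × (1.96 + 0.84)² × 40²/25² = 40.1, rounded up to 41 per group. The 25 points and SD 40 are reused below.

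**Assumptions for size.** The documents give neither a missed-visit rate nor a day-14 distribution. Assumed: 40 per arm; PASS at 120 h with mean 60, SD 40; day 14 with mean 15, SD 15; correlation 0.4; scores floored at 0; missed visits completely at random and filled with the 120-h value.

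**Expected differences.** For a normal variable floored at 0, the mean is μΦ(μ/σ) + σφ(μ/σ).
- 120 h, μ = 60: 60 × 0.933 + 40 × 0.130 = 61.2
- 120 h, μ = 35 (25 points lower): 35 × 0.809 + 40 × 0.272 = 39.2
- Day 14, μ = 15: 15 × 0.841 + 15 × 0.242 = 16.2
- Day 14, μ = 5: 5 × 0.631 + 15 × 0.377 = 8.8

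The LOCF mean in an arm is (1 − p) × day-14 mean + p × 120-h mean, where p is the missed fraction.
- No effect, 30% missed: 0.7 × 16.2 + 0.3 × 61.2 = 29.7, against a true 16.2.
- Difference at 120 h only: p × (61.2 − 39.2) = 2.2 points at 10% and 6.6 at 30%.
- No effect anywhere, 20% v 40% missed: 0.2 × (61.2 − 16.2) = 9.0 points.
- True day-14 difference in the power rows below: 16.2 − 8.8 = 7.4, about 7.5 points, with the arms equal at 120 h.

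**Rejection rates by simulation (two-sided 0.05).**

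| Scenario | Missed | t-test, observed | t-test, LOCF | Mann-Whitney, LOCF |
|---|---|---|---|---|
| 120-h difference only | 10% both | about 5% | 7% | – |
| 120-h difference only | 30% both | about 5% | 18% | 12% |
| No effect, unequal attendance | 20% v 40% | about 5% | 25% | 19% |
| True day-14 difference | 10% both | 75% | 31% | 63% |
| True day-14 difference | 30% both | 64% | 12% | 32% |

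The first three rows are false positives; the last two are power.

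**The case against.** No passage mentions LOCF and day 14 together. The protocol sentence belongs to the primary analysis, and Protocol 7.5.1 ties LOCF to discharge before day 5, so the authors may never have meant the rule to reach follow-up. That stands as a reading of intent. It does not change what SAP 6.3 says, and no other rule for a missed follow-up is given.

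The SAP's rationale carries no day-5 limit, so a patient who went home well and skips day 14 arguably falls within it. The SAP also keeps the option of other methods. Both points are fair. But recovery at discharge is assumed rather than shown to hold at day 14, it fits poorly the patients infused for most of five days, and the fallback names no method and no firm trigger.

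A reader might infer that non-attendance is likely. The documents support only that patients are invited. Their one allowance, 41 to 45 per group (4/45 = 8.9%), is for dropouts. At 10% missed, false positives are close to nominal.

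The simulation is simpler than the plan. It uses single-visit tests where SAP 6.2 plans a baseline-adjusted mixed model. Because missing values were generated completely at random, the observed-data comparison is unbiased by construction. The recommended mixed model was not simulated, and no cytokine figure was derived. Mann-Whitney, which the SAP uses when normality fails, softens the results.

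**Conclusion.** The point holds as a matter of wording: SAP 6.3 as written would fill a missed 14-day PASS score, pain rating or inflammatory marker with the last earlier value. For PASS and markers that value is nominally 9 days old (about 7 to 11 with windows), and 12 days if last taken at 48 h.

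The size depends on the assumed distributions and an undocumented missed-visit rate. False-positive inflation is slight at 10% missed and material at 30% or with unequal attendance. Loss of power is the sturdier harm, since it is already large by t-test at 10% missed. That result assumes equal arms at 120 h; a 120-h difference in the same direction would offset some of the loss, at the price of a biased estimate.

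Two stronger readings are not supported. One is that the primary result is compromised. The 48-h value is not filled from day 14. SAP 6.1 does make the 48-h comparison conditional on the mixed model, but it does not say whether day 14 is one of that model's time points. The other is that a patient still admitted on day 14 must receive the 120-h value. Table 1 and SAP section 5 schedule day-14 PASS with no discharge condition.

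This affects one visit of secondary and exploratory outcomes. It should be corrected before unblinding, the deadline Protocol 9.3.2 sets for missing-data handling.

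**What to change.** In SAP 6.3, with matching words in Protocol 9.3, restrict LOCF to the treatment period at most and state that it is not applied to the 14-day visit. Analyse day-14 PASS, pain and inflammatory markers from observed values in the planned repeated-measures mixed model, with visit as a categorical factor and day 14 named as one of its levels. Missing day-14 values are then handled as missing at random given the earlier measurements. Report day-14 attendance by arm.

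The cost is wording only; sample size and visit schedule do not change. The downside is that the day-14 estimate relies on missing at random and rests on fewer observed values.

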### 7.4.2. Secondary endpoints

- Difference in daily **PASS scores** between subgroups
- Difference in daily assessments of circulating **pro- and anti-inflammatory markers** (including CRP, IL-6, IL-8, IL-18, TNF- $\alpha$  and CD163) as well as **intestinal barrier markers** between subgroups
- Difference in **intestinal permeability** between subgroups measured from 48 to 72 hours after randomization using the oral polyethylene glycol 400/4000 test
- Difference in **intestinal motility** assessed by means of gut/colon transit using a CT-based radiopaque marker method on day 5 (+/- 1 day) between subgroups
- Difference in **pancreatic complications** (e.g. edema, fluid collections and necrosis) assessed and quantified with contrast-enhanced CT on day 5 (+/- 1 day) after randomization (20)
- Difference between subgroups in the following **clinical outcome parameters**: pain intensity and gut function (assessed by questionnaires), quantification of analgesics (separated into opioids and non-opioids), need for nutritional support, disease severity, invasive treatments, intensive care and hospital stay, as well as mortality during total hospitalization
- Difference in **health resource utilization** during hospitalization between subgroups

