### 9.1.5. Imaging

Patients with AP will have an abdominal contrast enhanced CT scan performed at baseline and after 5 days (+/- 1 day) of treatment. Morphological changes related to AP will be evaluated and described according to the terminology and definitions of the revised Atlanta criteria and the modified CT severity index (20,29).

Furthermore, as an integrated part of the CT exam at day 5 (+/- 1 day) patients will undergo assessment of the intestinal transit time using radiopaque markers given orally on day 3 prior to the CT exam.

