- Pre-existing renal insufficiency (defined as habitual estimated glomerular filtration rate (eGFR) below 45 ml/min/1,73m²)
- End-stage renal impairment requiring dialysis prior to inclusion
- Severe pre-existing comorbidities (assessed by investigator upon inclusion)
- Severe non-pancreaticobiliary infections or sepsis caused by non-pancreaticobiliary disease
- Child-Pugh class B or C liver cirrhosis
- Lactating

5. Data handling

Outcome	Source	Data collection rate	Datatype
PASS-score	From the patients' medical records (vital signs, lab results, quantification of need for opioid treatment), self-reported pain intensity and self-reported tolerance to solid foods	Daily during treatment and at 14-day follow-up	Ratio
Disease severity	Stratified as mild/moderate/severe using information about complications and organ failure from medical files	At 14-day follow-up	Ordinal
Subjective measures of pain intensity	Questionnaire: Pain intensity (current + worst/least pain the past 24 hours using NRS), pain interference score (7 parameters, scores 0-10)	Daily during treatment and at 14-day follow-up	Ordinal
Length of admission	Medical records, no. of days	90 days after randomization	Ratio
Mortality	Medical records; deceased y/n	90 days after randomization	Nominal
Circulating levels of pro- and anti-inflammatory cytokines,	Blood samples	Daily during treatment and at 14-day follow-up	Ratio
Intestinal permeability, gut transit time	Urine samples, CT-scans	Once during treatment (day 2-3)	Ratio
Prevalence of pancreatic complications	Stratified according to the revised Atlanta criteria (21) based on CT-scan	On day 5	Ordinal

Table 1

Delegated trial personnel at each trial center will register the collected data in the electronic case report form (eCRF) using the electronic data capture tool REDCap (Research Electronic Data Capture, version 10.6.26) hosted by the organization of The North Denmark Region. REDCap is a secure browser-based software, which meets all regulatory safety requirements (22,23). Data recording will begin when a participant is included and will occur gradually to the end of the trial. A detailed record of any corrections will be kept within REDCap. REDCap also contains features to improve data validation in the form of predefined variable ranges, options to detect that dates are in correct order and warnings if the forms are not sufficiently filled in.

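### The day-5 CT comparison ignores the baseline CT planned for every patient, which gives up precision and power but does not bias the result

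*Protocol*

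**What the plan says.** Two scans are planned per patient. Protocol 7.5.1 states that "an abdominal contrast-enhanced CT study will be performed at inclusion and after conclusion of treatment at day 5", and Protocol 9.1.5 repeats this: "abdominal contrast enhanced CT scan performed at baseline and after 5 days (+/- 1 day) of treatment". The same section describes the findings by the "terminology and definitions of the revised Atlanta criteria and the modified CT severity index", without distinguishing the two scans.

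The endpoint uses only the second scan. Protocol 7.4.2 lists pancreatic complications as a secondary endpoint, "assessed and quantified with contrast-enhanced CT on day 5 (+/- 1 day) after randomization". SAP 2.3 moves the outcome to the exploratory list and words it as "Difference between groups on the prevalence of pancreatic complications assessed and quantified using a CT-scan according to the Atlanta criteria". SAP Table 1 (section 5) records it as ordinal, collected on day 5, with the source "Stratified according to the revised Atlanta criteria (21) based on CT-scan". That table has no entry for a baseline CT reading.

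For the analysis, Protocol 9.3 says: "Outcomes assessed at single time points (baseline characteristics, CT features and gut permeability) are compared" by Student's t-test or a non-parametric test, and assigns binary outcomes to Fisher's exact test. In SAP 6.2, neither the single-time-point paragraph nor the counted-data paragraph names CT complications.

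Baseline adjustment is specified for PASS in SAP 6.1. SAP 6.2 extends that model to repeatedly measured outcomes, and CT is not among them. Protocol 9.3 also has a general clause allowing covariate analyses where applicable, but it does not mention baseline CT. The carry-forward rule for missing values in SAP 6.3 could at most let a baseline scan stand in for a missing day-5 scan. That is not adjustment.

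**The concern.** CT findings at day 5 depend partly on how severe the pancreatitis already looked at entry. Variation between patients that was present at randomization is noise in a comparison of arms, and a baseline measurement on the same scale can remove part of it. The plan pays for that measurement in radiation, cost and reading time, and then does not use it.

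With 45 patients per arm and randomization without stratification (SAP 3.2), chance differences in baseline CT severity are to be expected. An unadjusted test covers them with a wider standard error; an adjusted one removes the part that baseline predicts. At stake is the chance of detecting a real effect on pancreatic morphology, in a trial whose size was set for a different endpoint. The plan already accepts this reasoning for PASS.

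**Working it through.** **Inputs from the documents.** 45 patients per arm, two-sided alpha 0.05, 80% power (Protocol 7.6, SAP 3.1); CT at baseline and day 5 (Protocol 7.5.1, 9.1.5). No sample size, SD, baseline-to-day-5 correlation or complication rate is given for CT, so the correlation rho and the risks below are assumptions.

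**The plan's own figure.** For PASS, n per arm = 2 × (1.960 + 0.842)² × (40/25)² = 40.2, rounded up to 41, as stated. This point does not affect it.

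**Continuous CT score, no adjustment.** SE of the difference between arms = √(2/45) = 0.211 SD. Difference detectable with 80% power = 2.802 × 0.211 = 0.59 SD.

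**Continuous CT score, ANCOVA on baseline.** The variance is multiplied by 1 - rho², the SE by √(1 - rho²), and the equivalent unadjusted total is 90/(1 - rho²).

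| Assumed rho | Variance factor | Variance reduction | SE factor | Detectable difference (SD) | Power at 0.59 SD | Equivalent total |
|---|---|---|---|---|---|---|
| 0.2 | 0.96 | 4% | 0.98 | 0.58 | 82% | 94 |
| 0.3 | 0.91 | 9% | 0.95 | 0.56 | 84% | 99 |
| 0.5 | 0.75 | 25% | 0.87 | 0.51 | 90% | 120 |
| 0.7 | 0.51 | 51% | 0.71 | 0.42 | 98% | 176 |

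These rows assume 90 complete pairs. Fewer are likely: Protocol 9.3 makes secondary analyses per-protocol, and a patient discharged early is only offered the day-5 scan (Protocol 7.5.1, SAP 6.3). The variance factors do not depend on the number of pairs; the detectable differences and equivalent totals do.

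**Chance imbalance.** The baseline difference between arms also has an SE of 0.21 SD. An imbalance of one SE moves the unadjusted day-5 difference by rho × 0.211: 0.04 SD at rho 0.2, 0.11 SD at 0.5 and 0.15 SD at 0.7.

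**Categorical outcome.** The factor 1 - rho² does not carry over to a log-odds ratio. As an illustration, assume a finding present at baseline in 40% of each arm (18 of 45) and a common odds ratio of 0.375, so ln = -0.98.

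- *Strong baseline effect.* Control day-5 risks are 80% with the finding at baseline and 30% without; the treated risks are then 60% and 13.8%. Overall risks are 0.4 × 80 + 0.6 × 30 = 50% and 0.4 × 60 + 0.6 × 13.8 = 32.3%.
  - Unadjusted: log-odds ratio -0.74; SE = √[1/(45 × 0.50 × 0.50) + 1/(45 × 0.323 × 0.677)] = 0.44; |z| = 1.69; power about 40%.
  - Adjusted: variance 0.579 in the 18 per arm with the finding and 0.487 in the 27 without, so SE = 1/√(1/0.579 + 1/0.487) = 0.51; |z| = 0.98/0.51 = 1.91; power about 48%.
- *Weak baseline effect.* Control risks are 60% and 40%, treated 36% and 20%. By the same steps the SE goes from 0.45 to 0.46 and power from about 55% to 57%.

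So adjustment raises power while the SE of the log-odds ratio grows, because the adjusted log-odds ratio lies further from zero.

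**The case against.** **Randomization already deals with this.** It balances baseline CT findings in expectation, and the unadjusted SE and p-value allow for chance imbalance. This stands: the planned test is valid, and the issue is efficiency. A reader might infer that the comparison is biased because the arms may differ at baseline; the documents do not support that. Per-protocol selection and optional day-5 scans could disturb the balance, but that is a separate matter that omitting the covariate does not cause.

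**Complications present before randomization counted as outcomes.** A reader might infer that oedema, collections or necrosis seen at entry cannot reflect treatment and so contaminate the day-5 prevalence. The protocol's endpoint is day-5 status, assessed and quantified, and oedema or a collection can resolve, persist or grow differently by arm. Dilution figures can be produced: with new-complication risks of 40% versus 20% and 20 to 60% of patients affected at baseline, the 20-point difference shrinks to between 16 and 8 points. They rest on the assumption that every baseline finding persists to day 5, for which the documents give no support.

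**The gain may be small.** This also stands. Nothing in the documents excludes a rho of 0.2 or 0.3, where the gain is 4% or 9%. Quoting only the high end, such as rho 0.8 with 90/0.36 = 250 equivalent patients, would mislead.

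**The endpoint ranks low.** The SAP lists it as exploratory, which limits how much this matters. It is no reason to leave the analysis unspecified or to discard a covariate already collected.

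**Conclusion.** The concern holds as a loss of precision and power, and as a gap in the SAP, which names no test for CT complications. For a continuous score the variance reduction forgone is 4 to 51% over an assumed rho of 0.2 to 0.7. For Atlanta categories the gain is in power only, from about 2 to 8 percentage points in the two illustrations, and it depends on how strongly baseline status predicts day-5 status. Both ranges rest on assumed values and on 45 complete pairs per arm. The primary endpoint, the sample size and the SAP's own secondary outcomes do not change. The amendment is worth making because it is cheap, not because the planned test is wrong.

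**What to change.** In SAP 6.2, add a paragraph for the CT outcomes:

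- Analyse the day-5 modified CT severity index by ANCOVA, with treatment arm and the baseline CT score as terms. A covariate is preferable to a change score, whose variance factor 2(1 - rho) beats the unadjusted comparison only when rho exceeds 0.5 and is never below 1 - rho².
- Analyse the Atlanta-based categories by ordinal regression, or a single complication by logistic regression, adjusted for baseline CT status. State that the adjusted odds ratio is conditional on baseline.
- Keep day-5 status as the endpoint. New or worsened complications since baseline may be tabulated as a supportive description. As a replacement they would change the question, because improvement would no longer count.

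In SAP Table 1, add the baseline CT reading as a collected variable, and name the modified CT severity index, which at present appears only in Protocol 9.1.5. The results should report the number of patients with both scans, by arm.

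The cost is SAP wording, agreed before unblinding, and confirmation that baseline scans are read and recorded on the same scale. No extra scan or patient is needed.
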